Smooth Pursuit/ Neck Torsion: The patient is seated comfortably with the head positioned in neutral and is asked to follow a slow-moving target approximately 40° (20° to the right and to the left). The patient is instructed to keep the head still while observing the target. This is repeated in neutral and in cervical torsion (rotation of the trunk to the left or right underneath the head, rather than turning the head left or right). Differences in eye motion are noted with differences between neutral and cervical torsion being associated with cervical sensorimotor disturbance, as opposed to vestibulo-ocular impairment which may be more apparent in neutral [54].

Ethical considerations for clinical measures of neck function and head movement control: There is a risk of symptomatic aggravation such as increased dizziness or nausea, or soreness in the neck muscles following assessment based on previous participant reports, however all symptoms have been short-lived and (dizziness usually settles with a short break following test performance). Muscle endurance tests have the potential risk of mild muscle strain or post exercise soreness. However, there is minimal likelihood of injury as testing is performed within the participants tolerance levels. Any muscle discomfort or soreness associated with the endurance test is usually short lived and resolves within 24-48 hours. Participants will also

be offered a short break if required during testing to allow time for symptoms to settle.

Measures of vestibulo-ocular performance: will be used to identify individuals with evidence of vestibulo-ocular impairment [55]. Vestibulo-ocular assessment will commence with oculomotor screen of eye movement to determine presence or absence of baseline oculomotor paresis or palsy [56] which may unduly influence VOS results. This will be followed by completion of the oculomotor and vestibular testing suite (recorded as present/ absent: nystagmus, saccades, strabismus, canalith disorders, vestibulo-ocular reflex function impairment [gain]) on the ICS Chartr 200 VNG System (Otometrics; Taastrup; Denmark). Two or more positive tests will identify individuals with evidence of vestibulo-ocular impairment [57, 58].

Description of the vestibulo-ocular assessment is as follows:

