Participants identified as eligible for entry to treatment arm: will include those participants who demonstrate positive findings for a minimum of 3 cervical spine musculoskeletal and or sensorimotor outcome [12] as well as an absence of 2 or more positive oculomotor indicators of vestibulo-ocular impairment [55, 57]

Participants identified as ineligible for entry to treatment arm: identified due to an absence of sufficient positive neck related physical assessment findings, or alternately a positive

vestibulo-ocular screen will be provided with standardised graduated return to activity information [14, 70] as well as appropriate referral where evidence of vestibulo-ocular or physiological impairment is identified by the SC.

Of note, the SC conducting the laboratory-based screening session will be a New Zealand registered physiotherapist, and hold a current annual practicing certificate, Physiotherapy New Zealand membership, and ACC registration. They will hold additional training in OMT with a minimum of 3 years clinical experience. They will also have received specialised training from the PI (OG) in assessments to be used during the screening session including performance of testing, data reduction, and analysis of quantifiable outcomes necessary to establish participant eligibility for enrolment in the treatment arm of the study.

Estimated duration of total testing time will be 1.25 hour (1 hour for the SPE and 0.25 hours for induction and consent). All participants who provide consent and complete the SPE will be provided with a \$40 voucher to recognise the reasonable costs involved with participating in this study.

Treatment Sessions:

Treatment sessions procedure:

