Participants identified as eligible for allocation to the treatment arm of the study will be booked for their initial treatment session a maximum of 2 weeks following the screening session. Participants will be assessed during the first treatment session using an extended standardised assessment of the cervical spine (1 hour). Additional tests of musculoskeletal [31, 71] and sensorimotor function [72] as well as neural mechanosensitivity [73], standard to physiotherapy clinical practice in management of disorders of the neck and concussion [74], in addition to baseline results (provided in report form via post from the SC and supplied to the treating physiotherapist) will inform individualised treatment plans [18, 75]. Following initial assessment by the therapist, participants will receive treatment twice weekly for 4 weeks. During this time participants will also be requested to avoid alternate treatments for their concussion (except for use of prescribed medication/s) to minimise potential for confounding.

Interventions:

Treatment for management of identified neck impairments provided will include OMT (For e.g., Maitland, and Mulligan intervertebral joint mobilisation techniques) neuromuscular and sensorimotor retraining techniques standard to musculoskeletal physiotherapy practice internationally and in New Zealand for management of neck disorders [18, 75]. Individual treatment plans will be pragmatically determined. All participants receiving treatment will be provided with advice and education relating to graduated return to activity and prescribed a sub-symptom threshold cardiovascular exercise program using previously published

guidelines for exercise intensity dose [76]. This adjunct treatment aligns with internationally accepted standards of best practice for concussion management [4].

Treating physiotherapists, up-skilling, and treatment monitoring:

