Treating physiotherapists will be New Zealand registered, and hold current annual practicing certificates, Physiotherapy New Zealand membership, and ACC registration. They will hold additional training in OMT to at least diploma level with a minimum of 5 years clinical experience. Treating therapists will also participate in an initial 1 x 3 hour study induction session followed by 2 x 1 hour follow-up study review sessions (April to August). These sessions will be conducted by the PI (OG), a Masters (Musculoskeletal Physiotherapy) qualified physiotherapist, with 20+ years of clinical experience and expertise treating disorders of the neck including concussion, who is registered with the PNZ, and holds a current APC, and ACC registration. Sessions will provide physiotherapists treating patients in the study with an opportunity for continuing education related to concussion management. All sessions will be in person.

Follow up sessions:

Procedure:

Following completion of the treatment protocol all participants will be contacted by the SC and scheduled for follow-up review sessions (1 week and 3 months following completion of treatment sessions or if treatment sessions were not completed in full per-protocol follow up times). Follow-up sessions will be held at the same laboratories attended for the screening session. Participants will be requested to complete the same battery of questionnaires 1 day prior to attending each time and will also be examined using the SPE on both occasions. Participants will also be administered with activity monitors at each follow up and asked to wear these for a further 7 days and complete the daily activity and sleep logs. All participants completing these follow up sessions will be provided with a \$40 voucher to recognise the reasonable costs involved with participating in this study.

Nested Qualitative Focus Groups and Interviews:

Procedure:

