Clinical data will be entered directly into the study's online data recording form which only the PI, SC and members of the research team will be able to access. Data in this form will be stored under a unique identifier generated during the initial screening session with the SC. Where raw data requires further analysis, it will be deidentified (VR and VNG outcomes) and routinely uploaded to the PIs (OG) password protected laptop or the password protected study laptop. Data collected using VR and VNG will be collected on the devices using the participants unique identifier.

Statistical Analysis

Descriptive analyses will be performed on sociodemographic data. Exploration of central tendency of all data will be evaluated using Kolmogorov-Smirnov and Shapiro-Wilk tests. Where data is significantly skewed, attempts will be made to transform using suggested methods [57]. Individual demographic variables (sex, age, BMI, IPAQ score) which could reasonably be expected to influence quantitative outcomes will be analysed for significance using univariate linear regression and included in models.

Objective 1:

Quantified feasibility outcomes: activity, compliance, and adverse event monitoring

- a. Descriptive statistics will be used for recruitment frequency and the number of eligible participants, the drop-out rate, and degree of missing data for the patient rated and clinical outcomes measures. The programme will be considered feasible if 80% of patients complete the programme until formal discharge based on the physiotherapists' assessment and treatment documentation.
- b. Adherence to the intervention by auditing and summarising patients' logbooks and the physiotherapists' assessment and treatment documentation. The SC will audit the documentation. Adherence will be considered acceptable if 80% of exercises had been recorded in the patient's logbooks.
- c. Adverse events from the treatment will be determined by auditing the physiotherapists' assessment and treatment documentation as well as inclusion of formal reports submitted to the study or HEC in the event of serious adverse events. Number of events will be considered.
- d. Patient satisfaction score (/12) from the patient satisfaction exiting questionnaire will be calculated and mean and 95% CI will be reported.

Triangulation of qualitative (analysis described above) and quantitative outcomes [79] will determine overall feasibility of using the SPE to inform treatment management.

Objective 2:

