Linear mixed method analysis of repeated experimental outcomes will determine treatment effect. Effect modifiers including sex and age as well as statistically significant demographic confounders will be included in the final model. Further secondary analysis may be undertaken using data collected at all time points. Multivariable linear regression will identify items of the VOMS which best predict VNG OM.

Data storage:

All data (including patient and health practitioner data) will be stored on the personal password-protected laptops of the PI ([name]) and or the password-protected study laptop. Any hard copies of the questionnaires and consent forms will be stored in the PI's office in a secure filing cabinet. Only the researchers mentioned in the application and the SC (tba) responsible for processing and analysis will have access to the de-identified data collected during the study. The principal researcher ([name]) and the SC will keep a list identification codes with participant names, so that participants can be identified by their coded data if needed.

A standardised hard copy of the summary report of the participants findings from the screening session completed by the SC will be provided to the treating physiotherapist (via postal mail). This will not be de-identified since it will be used by the treating physiotherapist to inform treatment. A copy of these reports will be kept on the PI's personal password-protected laptop.

The treating physiotherapist will record the clinical assessment and treatments, as required, on their usual practice management systems as well as information related to study feasibility.

All data will be stored for the duration of the study on the primary investigator's password-protected University laptop and will be accessible by members of the research team. It will also be stored for at least 10 years in the school's archive folder on the High-Capacity Storage System (HCSS). Any personal information held about the participants (such as contact details and hard copy questionnaires) may be destroyed at completion of the research. Coded study information may be kept by the University of Otago in secure, cloud-based storage indefinitely. All storage will comply with NZ I data security guidelines.

Potential problems: (medical/legal; issues with disclosure; conflict of interest, etc)

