Today's date	4/5/11								
1. What time did you get into bed?	10:15 p.m.								
2. What time did you try to go to sleep?	11:30 p.m.								
3. How long did it take you to fall asleep?	55 min.								
4. How many times did you wake up, not counting your final awakening?	3 times								
5. In total, how long did these awakenings last?	1 hour 10 min.								
6. What time was your final awakening?	6:35 a.m.								
7. What time did you get out of bed for the day?	7:20 a.m.								
8. How would you rate the quality of your sleep?	 Very poor  Poor  Fair  Good  Very good	 Very poor  Poor  Fair  Good  Very good	 Very poor  Poor  Fair  Good  Very good	 Very poor  Poor  Fair  Good  Very good	 Very poor  Poor  Fair  Good  Very good	 Very poor  Poor  Fair  Good  Very good	 Very poor  Poor  Fair  Good  Very good	 Very poor  Poor  Fair  Good  Very good	
9. Comments (if applicable)	I have a cold								

(xi) *Participant Satisfaction Questionnaire*

1. Please rate how satisfied you were with the physiotherapy treatment you received.

1	2	3
Not satisfied	Satisfied	Very much satisfied

2. Please rate how satisfied with the frequency of the physiotherapy treatments.

1	2	3
Not enough	Just right	Too much

3. Please rate how satisfied you were with the duration of the treatments.

1	2	3
Too short	Long enough	Too long

4. Please rate how satisfied you were with the time spent with the physiotherapist during the treatments.

1	2	3
Not enough	Just right	Too much

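### Other concussion care is named as a confounder and participants are asked to avoid it, but no record of it is planned, and the single-group model is still said to establish a treatment effect

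*Protocol*

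**What the plan says.** Under Treatment sessions procedure, treatment is given twice weekly for 4 weeks, starting no more than 2 weeks after screening. Over those weeks "participants will also be requested to avoid alternate treatments for their concussion". Prescribed medication is exempt, and the stated reason is confounding.

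The records that the Protocol plans are these:

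- **Follow up sessions:** "Participants will be requested to complete the same battery of questionnaires 1 day prior to attending each time". The SPE, activity monitors and daily logs are also repeated, at 1 week and 3 months after treatment.
- **Quantified feasibility outcomes:** a home-exercise log, attendance, adverse reactions and an exit satisfaction questionnaire.
- **Statistical Analysis, Objective 1:** "Adherence will be considered acceptable if 80% of exercises had been recorded" in the logbooks. On the therapists' records and logbooks, "The SC will audit the documentation".
- **Data storage:** therapists record their assessment and treatments "on their usual practice management systems as well as information related to study feasibility".

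Study Design describes Part 1 as a single-group pretest-posttest study and Part 3 as the assessment of long-term effect at 3 months. Statistical Analysis, Objective 2, says that a linear mixed analysis of the repeated outcomes will establish the effect of treatment.

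**The concern.** The Protocol itself identifies other concussion care as a source of confounding and acts on it with a request, but plans no means of learning whether the request was followed. Other care is foreseeable from the document. Recruitment runs partly through physiotherapy, concussion and balance clinics, so some participants may already have a provider. The section on potential problems also allows for referral to a GP or physiotherapist when concerns persist after study sessions.

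Two things are at stake. First, any statement about adherence to the request would rest on what therapists happen to write down, and care after the last treatment has no planned source. This is a matter of data collection, so it cannot be left to an analysis plan. Second, Objective 2 reads change over time in one uncontrolled group as the effect of treatment. In people enrolled within 14 days of a concussion, that change also contains natural recovery, the wait before treatment and any other care.

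**Working it through.** **Plan's own figure.** The Protocol gives no number on other care. The only related count is group size, and it reproduces: 60 × (1 − 0.50) = 30 start treatment and 30 × (1 − 0.10) = 27 have data at all time points. The point does not depend on it.

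**Search for a planned record.** Each data source was checked for an item on other care or medication.

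| Source | What it is said to contain | Other care or medication? |
|---|---|---|
| 11 appended forms (the two PROMIS forms counted separately) | Symptoms, neck, dizziness, headache, fatigue, sleep, activity, quality of life, sleep diary, satisfaction | No item asks |
| Daytime activity log | Monitor removal, vigorous activity, an open-ended remainder | Not stated |
| Home-exercise log | Yes/no and minutes per day | Not stated |
| Therapist's study records | Attendance, adverse reactions | Not stated |
| Therapist's clinical notes | Own assessment and treatments, feasibility information | Possible, not stated |
| Experimental outcomes table | Named measures, list not closed | Not listed |
| Covariates considered | Sex, age, BMI, IPAQ score | Not listed |
| Sociodemographic questionnaire, online recording form | Content not shown | Unknown |

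The satisfaction form illustrates the first row. Its opening item is "Please rate how satisfied you were with the physiotherapy treatment you received", and the other three ask about the frequency, the duration and the therapist time of that same treatment.

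**Timeline.** Inputs are the wait of 0 to 2 weeks and the 4 weeks of treatment (Treatment sessions procedure), and visits 1 week and 3 months after treatment (Follow up sessions). Assumption: 3 months = 13 weeks.

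- (a) Screening to first treatment: 0 to 2 weeks
- (b) Treatment: 4 weeks, 2 × 4 = 8 sessions
- (c) Last treatment to the 1-week visit: 1 week
- (d) 1-week visit to 3-month visit: 13 − 1 = 12 weeks

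Total = a + b + c + d = 17 to 19 weeks. The request applies only in (b): 4/19 = 21% to 4/17 = 24% of the whole period. From screening to the 1-week visit, a + b + c = 5 to 7 weeks, of which the request covers 4/7 = 57% to 4/5 = 80%.

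This has two consequences. Baseline is measured at screening, so care during (a) falls inside the pre-post change although no request applies then. And a single undivided question at the 1-week visit would mix weeks under the request with weeks outside it, so it could not be read as adherence.

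**Design against wording.** Study Design calls Part 1 preliminary evidence on assessment and treatment combined. Objective 2 in the Statistical Analysis section goes further and has the model establish the treatment effect. With one group, no comparator and enrolment soon after injury, the time term in a mixed model estimates mean change. It does not separate treatment from recovery or from other care, and adjustment for sex, age and other demographic variables does not alter that.

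**The case against.** The strongest reply is that the request is sound, nothing contradicts it, and the complaint comes down to a field on a form that has not been described. Several forms are not shown: the sociodemographic questionnaire, the online recording form, the daytime activity log and the exercise log. The list of outcomes is also expressly open. Study staff see participants at the close of every period: the wait ends in a 1-hour therapist assessment, treatment brings twice-weekly contact, and both follow-ups are in person. The primary outcomes are feasibility outcomes, and none uses a rate of other care. Objective 2 is described elsewhere as preliminary. A new item also adds reading and recall for people whose symptoms may rise with screen time, as the Protocol warns.

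Much of this stands. It limits the point to what the Protocol plans and keeps the consequence low. It does not remove the point, because contact with participants is not a record, and the Protocol tells nobody to ask.

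A reader might infer three stronger things, none of which the documents support:

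- *That the results are biased by a known amount.* No rate or effect of other care is given.
- *That the 13 to 15 weeks outside the treatment period measure a failure of adherence.* No request applies in those weeks, so there is no adherence to fail.
- *That the request blocks needed referral for an eligible participant with one positive vestibular test.* The eligibility section mentions referral only for ineligible participants, but the Vestibular Oculomotor Screen text directs referral when impairment appears to be detected, without limiting it to them. Avoidance is requested and not imposed.

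**Conclusion.** The point holds in a limited form. The Protocol names other concussion care as a confounder and asks participants to avoid it for 4 of the 17 to 19 weeks observed, but plans no record of other care or medication in any period. This rests on the text and the forms shown; an unseen form could contain such an item. The 17 to 19 weeks assume that 3 months is 13 weeks.

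Separately, the Objective 2 statement is wrong as written, because a single-group pre-post model in recently injured people cannot establish a treatment effect. A record of other care would not cure that and would change no estimate. It would describe what accompanied the treatment and give the planned pilot randomised trial a co-intervention rate. The feasibility outcomes are unaffected. Both changes are optional, inexpensive improvements.

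**What to change.** 1. **Record other care.** At the 1-week visit, add a short item on other concussion, neck, vestibular or headache care, asked separately for before the first treatment, during the treatment weeks and since the last treatment. Filling in each participant's first and last treatment dates makes the split easier to answer. At the 3-month visit, ask about care since the 1-week visit. Record prescribed medication separately, because it is exempt. Report the treatment weeks descriptively as adherence to the request, and all periods as a co-intervention rate for the pilot trial. Do not estimate an effect of users against non-users.

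2. **Reword the inference.** In Statistical Analysis, Objective 2, and wherever Parts 1 and 3 are reported, describe the model results as change after SPE-based selection and treatment plus any other care, not as the effect of treatment.

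The cost is one short item at two existing visits, one descriptive table and a change of wording. The downsides are slightly more questionnaire burden for people with concussion, and recall error over 5 to 7 weeks at the first visit and about 12 weeks at the second.

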Study Design: This is a mixed methods feasibility study consisting of 3 parts and will investigate clinician and patient response to a ***simplified physical examination (SPE)*** used to inform post-concussion management. Part 1 (Experimental Study a.), a single-group pretest-posttest clinical design will provide preliminary (pilot) evidence of combined effect of assessment and treatment using the SPE to preselect those suited to manual treatment of the neck. Part 2 (Main Feasibility Study) a mixed methods study will consist of a nested qualitative study examining service providers attitudes toward use of the SPE to identify individuals appropriate for neck rehabilitation following concussion (Orthopedic Manual Treatment (OMT) and neuromuscular/ sensorimotor retraining) and utility of this method in the context of current practice. Quantitative exploration of patient compliance, and satisfaction, as well as any adverse reactions to treatment will also contribute to determining overall feasibility of using the SPE. Part 3 (Experimental Study b.), a 3-month follow up will assess long-term effect of treatment selection based on use of the SPE. Combined evidence from these studies will be used to inform development of a future protocol for a pilot randomised, non-inferiority, controlled trial.

Study Procedure and Setting: Participants will take part in one screening session in the Laboratories located at the School of Physiotherapy, University of Otago, Dunedin (referred to as “*screening session*”). Participants identified as eligible to enter the treatment arm of the study will then be invited to participate in further treatment session (referred to as “*treating sessions*”) where they will attend 2 physiotherapy sessions per week for 4 weeks at physiotherapy clinics local to Dunedin. Follow-up assessment (referred to as “*follow up sessions*”) for participants entering the treatment arm of the study will then be conducted 1 week and 3 months following cessation of treatment and will take place at the University of

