neck post-concussion [18] and with recommendations regarding pilot data sample sizes [19] so is considered adequate for this feasibility study.

Screening and Eligible Participant Identification Process:

Screening session procedure: The screening session will take place at the School of Physiotherapy research laboratories and will be conducted by the PI. Prior to attending the screening session participants will be sent a link by the SC to complete the battery of online questionnaires and asked to complete them 1 day prior to attendance. Included in the battery will be an electronic version of the consent form which participants will be required to sign prior to being able to access the questionnaires.

Questionnaires:

- Rivermead Post-concussion Symptoms Questionnaire (RPQ) [20] *13 Item and 3 Item* – Originally developed to provide an overall symptom severity measure based on symptom reporting following concussion. Participants rate the degree to which each symptom poses more of a problem since their head injury on a 0 to 4-point scale. When divided into three and thirteen item symptom scales construct validity was calculated at 0.83 for the 13-item questionnaire and 0.62 for the 3-item. IRR was 0.89 and 0.72 respectively [21]
- Neck Disability Index (NDI) [22] a 10 item scaled questionnaire. Each question requires the participant to select a response which most accurately reflects the difficulty they experience with specific functional tasks such as driving, reading working or sleeping, and also the extent to which they experience difficulty with function due to headache. It is currently utilised in cervical dysfunction populations including Whiplash Associated Disorder and neck pain to identify functional limitations resulting from either condition. Test-retest reliability has been established at 0.89 [22].
- Dizziness Handicap Index (DHI) [23] lists 25 functional activities. Individuals are asked to rate how much dizziness or unsteadiness affects performance of listed activities in terms of frequency. When summed the greatest resultant total scores for each of the subcategories; functional, emotional, or physical is determined to be the underlying causes for dizziness. Interrater reliability for the DHI has been calculated at 0.97 and internal consistency established between 0.72 and 0.85 for each of the categories [23]

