indirectly via the investigator's thumbs [44-46]. Based on previous studies using this method, [45, 47] determination of the presence of cervical intervertebral joint dysfunction as either "present" or "absent" is based on the presence of at least one joint being found to have all three of the following: 1/abnormal displacement, 2/abnormal tissue resistance to displacement (6-7/7 on a Likert scale) [44, 45, 48]) 3/ pain provocation reported ($\geq 3/10$ on a NRS) during the testing procedure [45, 48-50]). This criteria has previously been identified as an accurate indicator of cervical facet joint dysfunction in cervical spine disorders (sensitivity 71-100% and specificity 96-100%) [45, 47] and cervicogenic headache (sensitivity 80%) [32]. Intra and interrater reliability of manual assessment to identify individual cervical spine facet joint dysfunction is established at 0.63 to 0.85, and 0.79 to 0.96 respectively [44].

Joint Position Error (JPE): is generally considered a primary measure of proprioceptive capability of the cervical spine [51]. Participants are positioned in sitting with a low-level laser light attached to their head and centered on the middle of a target 90cm in front of them. Participants turn their head to the right and left and attempt to return as accurately as possible to their original start point while their eyes are closed. The use of laser beam to assess JPE of the neck is a common technique used by clinicians for patients with whiplash or neck pain and poses very minimal risks to the subjects. Significant difference between whiplash associated disorders D and control subjects has been identified with the cervical spine positioned to start in neutral [52]. Sensitivity for this test has been established in head neutral position at 78% and specificity at 85% in a neck pain cohort and interrater reliability at 0.68 [53].

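### Nothing keeps the baseline findings from whoever repeats the SPE at follow-up, which leaves the hands-on tests, chiefly the manual spinal examination, open to examiner expectation

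*Protocol*

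**What the plan says.** Under Study Design, Part 1 is described as "a single-group pretest-posttest clinical design will provide preliminary (pilot) evidence of combined effect of assessment and treatment". Under Study Procedure and Setting, follow-up "for participants entering the treatment arm of the study will then be conducted 1 week and 3 months following cessation of treatment", so only treated people return. Under Follow up sessions, they "will also be examined using the SPE on both occasions".

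On who examines at baseline, the protocol gives two answers. The Screening session procedure places the session at the "School of Physiotherapy research laboratories and will be conducted by the PI". The section Eligibility for Entry to Treatment Arm says "the SC conducting the laboratory-based screening session will be a New Zealand registered physiotherapist". The follow-up section names nobody.

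On access to earlier results, Data Management puts clinical data in one online form open to the PI, the SC and the research team. Data storage describes a "summary report of the participants findings from the screening session completed by the SC". It goes to the treating physiotherapist, and a copy stays on the PI's laptop.

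On how the key test is scored, the Manual Spinal Examination section calls a joint dysfunctional only if three criteria are all met: abnormal displacement, "abnormal tissue resistance to displacement (6-7/7 on a Likert scale"), and pain reported by the participant. The Experimental Outcomes table lists the result as positive or negative.

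**The concern.** The manual spinal examination turns largely on what the examiner feels through the thumbs. Two of its three criteria are the examiner's perception, and the result is binary, so a small shift in judgement on resistance can change the participant's result. An examiner who can look up which joints were positive before treatment, and who works in a study whose stated hypothesis is improvement, may score the repeat differently from one who cannot.

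A control arm examined in the same way would share much of that lean. Here there is none, and Objective 2 of the Statistical Analysis section takes the repeated outcomes as showing treatment effect. The results are also meant to inform a later randomised trial. The protocol already recognises this type of threat in the qualitative work, where it guards against the PI's beliefs shaping the themes. The physical re-examination has no equivalent safeguard.

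**Working it through.** There is no stated figure for this bias to reproduce. The check is a reading of the sections together, with arithmetic only for scale.

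**1. Is anything masked?** The protocol does not conceal baseline findings, visit or treatment status from the person repeating the SPE. The de-identification in Data Management removes the name from VR and VNG files. It does not bear on what the examiner can see when doing hands-on tests.

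**2. Could the follow-up examiner know the baseline result?** Yes, for either candidate. The PI and the SC can both open the form, the SC writes the report and the PI holds a copy. Whether the same person examines at both visits cannot be determined, because the protocol names two different baseline examiners and no follow-up examiner.

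**3. Which outcomes are exposed?**

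| Outcome | How it is obtained | Exposure |
|---|---|---|
| Manual spinal examination | Positive/negative; two of three criteria felt by the examiner | Main exposure |
| Smooth pursuit/neck torsion | Differences in eye motion noted by the observer; part of the SPE, but not itemised in the outcome table, which is declared non-exhaustive | Lesser |
| VR range, velocity, accuracy | Degrees and degrees per second from motion tracking | No reader judgement described |
| VNG overall (two or more positive tests) | Treatment entry requires fewer than two positive oculomotor indicators | Already negative at baseline, so cannot improve |
| VNG single tests | Present/absent, at most one positive per person at entry | At most one item per person can shift towards negative |
| Questionnaires | Self-report | Not examiner-judged |

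**4. What would hiding the baseline record conceal?** Entry requires at least three positive cervical musculoskeletal and/or sensorimotor findings, not a positive manual examination specifically. Anyone examining a returning participant therefore knows that the person was treated and had three or more positive neck findings. What can be hidden is which tests, and which joints, were positive.

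**5. Scale.** Study power gives 60 eligible, 50% declining and 10% dropping out: 60 × (1 − 0.50) = 30, and 30 × (1 − 0.10) = 27. This reproduces the protocol's 27. If all 27 have a manual examination result, one changed call moves the proportion positive by 1/27 = 3.7 percentage points.

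For illustration only, assume all 27 are positive at baseline, none truly changes, and calls shift in one direction only. The exact two-sided McNemar p-value for d shifted calls is 2 × 0.5^d: 0.0625 for d = 5 and 0.031 for d = 6 (6/27 = 22%). The binomial chance of at least six shifted calls is 0.047, 0.21, 0.46 and 0.86 if the probability of a shift per person is 10%, 15%, 20% and 30%. Those probabilities are assumed, and the protocol does not name McNemar's test. The spread from 0.047 to 0.86 shows why no size can be put on the bias.

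**The case against.** The best reply is that masking achieves little here. The examiner will always know that a returning participant was treated, and the hypothesis of improvement gives a direction to that knowledge. Sight of the baseline sheet has no fixed direction: an examiner might anchor on it and under-call real change. The outcomes are exploratory, the primary outcomes are feasibility outcomes, and natural recovery and regression to the mean are untouched by masking. All of this stands. It limits the gain to a modest one but does not remove it, because the examiner need not know which joints or tests were positive. Nor can the matter be left to an analysis plan: what the examiner sees is trial conduct, settled before data are collected.

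A reader might be tempted further, in four ways that the documents do not support.

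- Data Management says "Data collected using VR and VNG will be collected on the devices using the participants unique identifier", and the identifier is generated at the first screening session. One may infer that all visits share it. That is reasonable, though not stated. It is also no defect in itself, because repeated-measures analysis needs visits linked.
- One may infer that VR results can drift with the reader. They are instrument outputs.
- One may infer that VNG results will drift towards improvement overall. The entry rule rules that out for overall status and leaves at most one positive item per person.
- One may want a specific inflation of the apparent resolution rate. The protocol gives neither the number positive on the manual examination at baseline nor any rate of borderline calls.

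**Conclusion.** The point holds as a minor, inexpensive improvement, confined to the examiner-judged hands-on tests: chiefly the manual spinal examination and, less so, smooth pursuit/neck torsion. The protocol leaves baseline findings open to whoever repeats the SPE, and in a single group any resulting lean is counted as treatment effect. Its size cannot be quantified from the documents, and its direction is plausible rather than established. The 3.7 points per changed call assumes that all 27 expected completers contribute a result.

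The disagreement over who conducts the baseline examination, together with the missing follow-up examiner, is a plain textual inconsistency and needs correcting in any case.

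**What to change.** - In Follow up sessions and Data Management, state that the online form hides earlier-visit SPE findings and the baseline report from the examiner until the current hands-on SPE results are entered and locked.
- Reconcile the Screening session procedure, Eligibility for Entry to Treatment Arm and Follow up sessions so that each names who examines at each visit.
- Reading VNG recordings under a code that hides the visit is optional and of small value. If it is done, keep the immediate baseline reading for eligibility. VR recordings need no masked reading.

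The cost is form settings and some data-handling time, with no extra staff or visits. The examiner will still know that the participant was treated and met the entry rule, so the bias is reduced, not removed. Natural recovery and regression to the mean remain as limits of the single-group design and should be acknowledged when the change scores are interpreted.
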